#### **6.2.3.1 Implementation of dose escalation decisions**

To implement dose escalation decisions, the available toxicity information (including adverse events and laboratory abnormalities that are not DLTs), the recommendations from the BLRM, and the available PK information will all be evaluated by the Investigators and Novartis study personnel (including the study physician and statistician) during a dose decision meeting by teleconference. Drug administration at the next higher dose level may not proceed until the investigator receives written confirmation from Novartis indicating that the results of the previous dose level were evaluated and that it is permissible to proceed to a higher dose level.

#### **6.2.3.2 Intra-patient dose escalation**

Intra-patient dose escalation is not permitted at any time within the first 4 cycles of treatment. After the fourth cycle is completed, individual patients may be considered for treatment at a LDK378 dose higher than the dose to which they were initially assigned. In order for a patient to be treated at a higher dose of LDK378, he or she must have tolerated the lower dose for at least 4 cycles of therapy without any LDK378-related toxicity  $\geq$  CTCAE grade 2. The proposed higher dose must be a dose that has completed evaluation and has not exceeded the maximum tolerated dose (MTD). Novartis must be consulted prior to an intra-patient dose escalation, and agree with the escalation decision. There is no limit to the number of times a patient may have his or her dose of LDK378 increased. The dose change must be recorded on the DAR eCRF.

Data from the first cycle of treatment at the new dose level will not be formally included in the statistical model describing the relationship between dose and occurrence of DLT. However, these data will be incorporated into the clinical assessment of safety when escalation to a new dose level is considered for the study.

### 6.2.3.3 Changing from Fasted to Fed Dosing

Changing from fasted dosing to fed dosing is allowed after the patient has completed at least six cycles of fasted dosing, provided the following:

- The MTD/RDE in the fed state has been determined, and dosing with food has been chosen for further expansion
- The dose level of LDK378 must remain the same, or be reduced to the MTD/RDE in the fed state, if that is lower than the patient’s current dose
- The patient must have tolerated the fasted dose without any drug-related toxicity  $\geq$  Grade 3, except for nausea, vomiting, diarrhea or abdominal pain
- If a patient on the fasted dosing has had a drug-related toxicity of  $\geq$  Grade 3 other than nausea, vomiting, diarrhea or abdominal pain, the patient must have had a dose reduction and tolerated the reduced dose without a drug-related toxicity of  $\geq$  Grade 3 for at least two cycles before changing from fasting dosing to fed dosing

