CYP3A was identified as the major CYP isozyme responsible for the metabolism of LDK378. An inhibition DDI study conducted in healthy volunteers indicated that ketoconazole (200 mg bid for 14 days), a strong CYP3A inhibitor, increased the Cmax and AUCinf of a single 450 mg oral dose of LDK378 by 1.2-fold and 2.9-fold, respectively, compared with LDK378 alone [REDACTED]. Therefore, concurrent use of strong CYP3A inhibitors should be avoided. An induction DDI study conducted in healthy volunteers indicated that rifampin (600 mg daily for 14 days), a strong CYP3A inducer, decreased the Cmax and AUCinf of a single 750 mg oral dose of LDK378 by 44% and 70%, respectively, compared with LDK378 alone [REDACTED]. Concurrent use of strong CYP3A inducers should be avoided.

A food effect study was conducted in healthy volunteers [REDACTED]. Compared to the fasted state, a low-fat meal increased Cmax and AUCinf of a single oral dose of LDK378 500 mg in healthy subjects by 43% and 58%, respectively, whereas a high-fat meal increased Cmax and AUCinf by 41% and 73%, respectively.

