During the dose escalation parts of the study, dose escalation will be guided by the BLRM, but the maximum increase in dose for the fasted dose escalation part will be limited to 50% of the last prior dose level before reaching 450mg/m^2, and to 25% after reaching 450 mg/m^2, which is the MTD in adults, as shown in [Table 6-1](#). Dose escalation for the fed dose escalation part will be limited to a 25% or smaller increase above the prior fed dose level. These restrictions are necessary to prevent excessive escalation, since the starting dose is relatively close to the adult MTD.

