**Table 6-1 Provisional dose levels for fasted pediatric dose escalationa**

| Dose Level        | Provisional Daily Dose b | Increment from previous dose |
|-------------------|-------------------------------------|------------------------------|
| -1 c   | 200 mg/m                | 33% reduction                |
| 1 (starting dose) | 300 mg/m                | Starting dose                |
| 2                 | 450 mg/m                | 50% increase                 |
| 3                 | 560 mg/m                | 25% increase                 |
| 4                 | 700 mg/m                | 25% increase                 |
| 5                 | 875 mg/m                | 25% increase                 |
| 6                 | 1090 mg/m               | 25% increase                 |

a. This table is intended as an example for guidance for the dose escalation part only. Intermediate or higher dose levels may be used if the dose-escalation rules presented in this protocol are followed. Actual dose levels will be confirmed in writing by Novartis and provided to all participating study sites before treatment of patients in a new cohort.

b. All doses will be dosed on a mg/m^2 basis, rounded to the nearest 50 mg (refer to Section 6.1.1 for details).

c. Dose level -1 may be used if appropriate (e.g., if the starting dose level is not well tolerated).

The fasted dose escalation will continue until the MTD and/or the RDE dose is reached. Following completion of the dose escalation part of the study, a dose will be chosen for the expansion part of the study. The dose for the expansion part will be opened at either the fasted MTD, or a lower dose that is determined to be the RDE.

After the fasted dose escalation has reached the MTD and/or RDE, the fed dose escalation will begin. The starting dose for the fed dose escalation part will be approximately 63% of the fasted MTD determined in this study. This is based on the data from adult healthy volunteers

taking LDK378 with a low-fat meal. It is estimated that the steady state exposure of LDK378 with a low-fat meal will be increased 1.58 fold. Dose escalations during the fed dose escalation part of the study will be limited to a 25% or smaller increase above the prior fed dose level.

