2.1 Data analysis general information

Data will be analyzed by Novartis Oncology Biostatistics and Statistical Programming personnel according to the data analysis section 10 of the LDK378X2103 protocol, which will be available in Appendix 16.1.1 of the Clinical Study Report (CSR). Important information is

given in the following sections and details are provided, from which Appendix 16.1.9 of the CSR will be written.

The data will be analyzed using SAS version 9.4 or later, and for Bayesian modeling, R version 2.13.2 or later, and WinBUGS version 1.4.3 or later. The Bayesian modeling of the dose-toxicity relationship used for dose escalation decision making and inference for the MTD is performed using internal Novartis R library functions (OncoBayes) created by Novartis's Methodology group and are run using R version 2.13.2 or later in the MODESIM/GPSII environment.

Data from patients who signed study informed consent in centers that participate in this study will be used in the analysis; due to expected small size of enrollment at individual centers, no center effect will be assessed. Each analysis will use all data in the database up to the analysis cutoff date, determined prior to database lock. Data collected after patients' withdrawal of informed consent for further participation in the study will not be reported (except for death date which might be obtained from public records).

Final CSR

The study data will be analyzed and reported based on all patients' data of both dose escalation and expansion parts at the end of study, and a final CSR will be written. Patients treated with the MTD, or RDE if different, on the regimen (fasted or fed) during the dose escalation part, will be pooled with those receiving both the same dose and the same regimen during the expansion part. For patients undergoing intra-patient dose escalation to doses other than their initially received dose level, their post-escalation data will be listed separately. However, only data before the first intra-patient escalation will be used in summary statistics. A treatment group is defined by dose level and regimen (fasted or fed).

End of study is defined as earliest occurrence of one of the following:

1. All patients have discontinued study treatment, and all required Study evaluation completion (SEC) follow-up visit have been completed, or

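### Safety and exposure data collected after a fasted-to-fed switch stay in the fasted group, because the summaries have no cut-off for a change of regimen

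*Protocol*

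**What the plan says.** Protocol 6.2.3.3 permits a lasting change of regimen: "Changing from fasted dosing to fed dosing is allowed after the patient has completed at least six cycles of fasted dosing". The fed MTD/RDE must be known and fed dosing must have been chosen for further expansion. On dose, "The dose level of LDK378 must remain the same, or be reduced to the MTD/RDE in the fed state", the reduction applying where the fed level is lower than the current dose. The rationale for Amendment 6 records that fed dosing was chosen to complete the expansion.

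SAP 2.1 says "A treatment group is defined by dose level and regimen (fasted or fed"). For patients whose dose is escalated, it says that "only data before the first intra-patient escalation will be used in summary statistics", with later data listed separately. Protocol section 10 has the same rule. Neither document gives a matching rule for a change of regimen.

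Group assignment is spread over several places in the SAP:

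- **2.1.1:** the group is generally the dose and regimen planned at Cycle 1 Day 1. For safety it is to reflect what was received, regimen included, and the reader is sent to 2.2 for the method.
- **2.2, full analysis set:** planned treatment comes from the first dosing record, and fasted or fed is read from the dose level in Table 2-1.
- **2.2, safety set:** the planned level stands if any daily dose matched it. Otherwise the first actual dose is mapped to the nearest planned level. Meal state is not tested.
- **2.8:** the on-treatment window runs to 30 days after the last dose.

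**The concern.** Regimen is half of the definition of a treatment group, but a change of regimen has no consequence in the tables. A patient who starts fasted, switches after six cycles and stays on drug remains one fasted patient throughout, including the months on fed dosing. SAP 2.1.1 and SAP 2.2 do not agree: the first says regimen received will count for safety, and the second supplies an algorithm that cannot see it.

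The secondary safety objective is to characterise safety and tolerability in the fasted and the fed state, and Amendment 3 added the fed part because of gastrointestinal symptoms. The table conventions make the allocation matter. Adverse events are shown at the patient's maximum grade (SAP 2.8.1), and laboratory and QT shift tables use the worst post-baseline value (SAP 2.8.2 and 2.8.3.1). In these tables a post-switch observation can only leave the fasted result unchanged or worsen it. ECGs continue throughout treatment (Protocol Table 7-4), and Protocol 2.6 describes QTc prolongation as concentration-dependent, so the ECG tables are included.

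**Working it through.** **Inputs**

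- Food effect used for planning (Protocol 6.2.2): "It is estimated that the steady state exposure of LDK378 with a low-fat meal will be increased 1.58 fold".
- Its source (Protocol 1.2.1.2.4): a low-fat meal raised Cmax and AUCinf of a single 500 mg dose "in healthy subjects by 43% and 58%, respectively".
- Recommended doses (SAP 2.5): 510 mg/m² fasted, 500 mg/m² fed.
- Dose-step limits (Protocol 2.3). Fasted part: "the maximum increase in dose for the fasted dose escalation part will be limited to 50% of the last prior dose level" below 450 mg/m², and 25% from there. Fed part: "Dose escalation for the fed dose escalation part will be limited to a 25% or smaller increase above the prior fed dose level".

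**The plan's own figure.** The fed starting dose is set at about 63% of the fasted MTD. 1/1.58 = 0.633, and 0.63 × 510 = 321 mg/m², which matches the 320 mg/m² fed level in SAP Table 2-1. The figure reproduces.

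**Exposure change at a switch.** Let d be the fasted dose before the switch. The dose after it is min(d, 500), and exposure is assumed proportional to dose.

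AUC ratio = 1.58 × min(d, 500)/d. Cmax ratio = 1.43 × min(d, 500)/d.

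| Fasted dose (mg/m²) | Dose after switch | AUC ratio | Cmax ratio |
|---|---|---|---|
| 200, 300 or 450 | unchanged | 1.58 (+58%) | 1.43 (+43%) |
| 510 | 500 | 1.58 × 500/510 = 1.549 (+55%) | 1.402 (+40%) |
| 560 | 500 | 1.58 × 500/560 = 1.411 (+41%) | 1.277 (+28%) |

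**Dose steps for scale.** Among the fasted levels in SAP Table 2-1: 300 to 450 is +50%, 450 to 510 is +13.3%, 510 to 560 is +9.8%. A multi-level escalation from 300 to 510 is +70%. An escalation from 450 to 510 removes later data from the summaries. A switch at 450, with a planned AUC change of +58%, does not.

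**Sensitivity to the food effect.** The switch equals a 25% step when the food effect is 1.25 (dose kept), 1.25 × 510/500 = 1.275 (510 to 500), or 1.25 × 560/500 = 1.40 (560 to 500). Below these values it is smaller than a 25% step.

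**How many patients.** The documents do not say. A ceiling follows from the amendment histories. On 17 February 2016, 45 − 34 = 11 patients were on treatment. Fasted expansion patients later rose from 5 to 7, adding 2. That gives at most 13 of 25 + 7 = 32 fasted patients (41%). It is generous, because it counts all 11 as fasted although fed escalation was then under way. The range is 0 to 13.

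**What is not touched.** DLTs and the BLRM use Cycle 1 only. PK samples are evaluable only under the originally assigned prandial condition (SAP 2.2). The last scheduled sample is Cycle 4 Day 1 in Protocol Table 7-5 (day 64), or Cycle 6 Day 1 in SAP 2.10 (day 106). Both fall before six cycles are complete (6 × 21 = 126 days).

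**The case against.** The best defence starts with SAP 2.1.1, which does name regimen received as the basis for safety grouping, so it would be wrong to say that the SAP simply fixes the safety group at Cycle 1 Day 1. That sentence stands as intent. It does not settle the matter, because the method it points to works on dose level and gives each patient one group for the whole study.

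Second, a reader might infer that a switch changes exposure by more than any dose step. The documents do not support that. The 1.58 comes from one dose in healthy adults with a low-fat meal. Fed patients here take a 100 to 300 calorie snack, and fasted patients also take the drug with a spoonful or two of food (Protocol 6.1.2). The recommended doses came out nearly equal, which hints at a smaller effect without proving equal exposure. Even on the planning figures, the Cmax change and the 560 to 500 switch fall below a 50% step, and an escalation from 300 to 510 exceeds the switch. At steady state, trough rises more than dose-proportionally (Protocol 1.2.1.2.4), so nominal dose steps understate exposure changes.

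Third, the effect on tables may be small. A post-switch event counts only if it is a new term or a higher grade than anything in the preceding 126 or more days, and Protocol 6.2.3.3 requires that the fasted dose, or a reduced one, was tolerated, gastrointestinal symptoms apart. No formal fasted-versus-fed test is planned. This limits the size of the problem but does not remove the mislabelling.

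Finally, keeping all on-treatment data under the initial group is a legitimate choice, and data after dose reductions do stay in. But the plan does not state that choice for regimen switches, and it conflicts with SAP 2.1.1.

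**Conclusion.** The point holds as a gap in the safety and exposure summaries. Followed as written, the SAP counts fed-state adverse events, laboratory values, ECGs and dosing of switchers in the fasted group. This follows from the assignment rules together with the absence of any switch rule; no single sentence says so.

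On the planning factor, the AUC change would be about +41% to +58%, assuming dose proportionality and that adult single-dose data carry over to children at steady state. It may be smaller. The mislabelling itself does not depend on the size of the food effect.

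Two further readings should be avoided. One is that switchers supply much of the late fasted exposure: the documents give neither their number nor their share, and both may be zero. The other is that the MTD/RDE, the choice of regimen or the PK results are contaminated. A switch is possible only after the fed dose is set and fed dosing chosen, and the DLT and scheduled PK data precede it. This deserves correction but does not threaten the primary objective.

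**What to change.** In SAP 2.1 and 2.2, state that by-group adverse event, laboratory, ECG and exposure summaries use data up to the earlier of the first intra-patient dose escalation and the first fasted-to-fed switch. List post-switch data separately and report the number of switchers by initial group. Bring the safety-set rule in SAP 2.2 into line with the regimen wording in SAP 2.1.1.

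Leave ORR, DOR and PFS by initial regimen. This is narrower than the existing escalation rule, which makes no exception for efficacy. The reason is that only patients who have completed six cycles can switch, so ending efficacy follow-up at that point would select on outcome.

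The wording costs a few sentences and the programming a date cut. There are two real costs. Some late safety data from a small paediatric study move from tables to listings. The sponsor must also confirm that switch dates exist in the database or source records. Protocol 6.2.3.3 names no form for them, meal records are tied to PK days (Protocol 7.3.1), and a 510 to 500 change can vanish in rounding: at a BSA of 1.0 m² both give 500 mg.

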### 6.2.4 Definitions of dose limiting toxicities (DLTs)

A DLT is defined as an adverse event or abnormal laboratory value assessed as unrelated to disease, disease progression, inter-current illness, or concomitant therapies that occurs within the first 21 days (Cycle 1) of treatment with LDK378 and meets any of the criteria included in [Table 6-2](#). Any adverse event is not considered a DLT if it does not happen within the first 21 days of treatment. However, medically significant events should be followed up as for DLTs. NCI CTCAE version 4.03 will be used for all grading. For the purpose of dose-escalation decisions, DLTs will be considered and included in the BLRM.

The investigator must notify Novartis immediately of any unexpected CTCAE grade  $\geq 3$  adverse events or laboratory abnormalities. Prior to enrolling patients into a higher dose level, CTCAE grade  $\geq 2$  adverse events will be reviewed for all patients at the current dose level

**Table 6-2 Criteria for defining dose-limiting toxicities**

**Any adverse event of CTCAE grade 3 or higher during cycle 1 is a DLT, with the following exceptions**

|            |  |
|------------|--|
| Hematology | 
 
• Neutropenia is a DLT if it is CTCAE grade 4 lasting > 7 days
 
• Thrombocytopenia is a DLT if it is CTCAE grade 3 lasting > 7 days or CTCAE grade 4 thrombocytopenia at any time
 
• Anemia is a DLT if it is CTCAE grade 4 lasting > 7 days
 
• Lymphopenia is a DLT if it is CTCAE grade 4
 
 |
| Renal      | 
 
• Serum creatinine > 2 x ULN is a DLT Refer to Table 6-5 for additional follow up.
 
  |
| Hepatic    | 
 
• AST or ALT increase is a DLT if CTCAE grade 3 or greater
 
• Total bilirubin is CTCAE grade 2 with AST or ALT CTCAE grade 1 in the absence of cholestasis or hemolysis. Refer to Table 6-5 for additional follow up.
 
  |
| Pulmonary  | 
 
• Pneumonitis or ILD of any grade without infectious etiology is a DLT
 
   |

**Any adverse event of CTCAE grade 3 or higher during cycle 1 is a DLT, with the following exceptions**

|   |  |
|---|--|
| Gastrointestinal                                    | 
 
Nausea and vomiting are DLTs if they are <math>\geq</math> CTCAE grade 2 despite optimal anti-emetic therapy
 
Amylase and/or lipase elevation <math>\geq</math> grade 3 is a DLT. Refer to Table 6-5 for additional follow up.
 
Diarrhea is a DLT if it is <math>\geq</math> CTCAE grade 3 despite optimal anti-diarrhea treatment
 
 |
| Infection   | 
 
Infection or fever in the absence of neutropenia are DLTs if they are <math>\geq</math> CTCAE grade 3 and last <math>></math> 5 days
 
  |
| Electrolytes  | 
 
Hypophosphatemia is a DLT if it is <math>\geq</math> CTCAE grade 3 and lasts <math>></math> 7 days
 
  |
| Fatigue   | 
 
Fatigue is a DLT if it is <math>\geq</math> CTCAE grade 3 and lasts <math>></math> 7 days
 
   |
| Other adverse events                                | Other unacceptable toxicities may be considered to be DLTs by the Investigators and Novartis, even if not CTCAE grade 3 or higher  |
| Any toxicity resulting in an excess of missed doses | Inability to deliver $\geq$ 75% of the planned doses in a treatment cycle (i.e. at least 16 doses in a 21 day cycle) because of toxicity at least possibly related to LDK378 is a DLT  |

CTCAE version 4.03 will be used for all grading.

Patients may receive supportive care as per local institutional guidelines.

Optimal therapy for vomiting or diarrhea will be based on institutional guidelines, with consideration of the prohibited medications listed in this protocol.

## Dose modification related to DLTs

If a patient experiences a DLT, treatment with LDK378 should be held. Following resolution of the toxicity to grade 1 or to the patient's baseline value the patient may resume treatment with LDK378. In general patients who resume therapy following a DLT should resume at a lower dose level assessed to be safe with a minimum dose reduction of 50 mg. However, following recovery of a DLT that was not considered clinically important or can be managed if it recurs (e.g., replacement of an electrolyte), the patient may resume therapy without dose reduction, if the investigator considers that to be in the best interest of the patient. The dose should not be reduced below 150 mg/m^2. Provisional dose levels for LDK378 are listed in [Table 6-1](#).

